
Section 5.0 Research Design

5A) Introduction to the Research Design of Proposed Project

We propose a three-arm, repeated measures RCT for persons undergoing NSCLC surgery as shown in **Fig 8**. The design provides for **efficacy** comparisons of outcome measures among the immediate (exercise) intervention group (IIG), the wait-list control group (WCG) usual care, and the attention control group (ACG) by age after 6 wks (**Aim 1**) through the measurement of primary and secondary outcomes. The design also provides for evaluation of the timing of the intervention (**Aim 2**) by comparing study outcomes of the IIG's wks 1-6 with those of the WCG's wks 7-12 by age to account for time since surgery. Note that the timing of the data collection occurs near the time of the assessment during the week when the assessment is conducted. For example, if a participant has an unexpected visitor at their home and would like to have the data collector call the next day, then the data collector may call the next day. Unlike mice or non-human studies, we need to balance absolute timing against the needs of our human participants so we incorporate some flexibility required of our human participants when collecting data. Determining optimal timing to initiate an exercise program for post-surgical NSCLC patients is needed. We chose to start the WCG intervention at 6-wks post-hospital discharge based on Leach et al.'s¹¹³ findings that 43% of the 66 postsurgical NSCLC patients in their study preferred to start an exercise program during adjuvant treatment. Also, adjuvant treatment (radiation and/or chemotherapy) commonly begins 4-10 wks after surgery, with nearly 30% of patients undergoing adjuvant treatment¹¹⁴ Sustainability of the intervention (**Aim 3**) can be determined by offering the IIG the option to extend their exercise to 12 wks and calculating the percent that elect to extend, assessing acceptability, adherence, and retention while measuring primary and secondary outcomes for efficacy. Adverse events will be monitored to provide for safety (R21 RCT reported no adverse events).

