
5C2a) WCG participants will have baseline data collected pre-surgery by the nurse recruiter and receive a pedometer and instructions for recording total steps/day in Daily Diary (Appendix A7). The WCG nurse intervener (nurse) will visit in the hospital post-surgery to review study trajectory. Research staff will contact WCG by phone within approximately 24 hrs of discharge to collect post-surgery data (if too ill, data collection rescheduled within 3 days of discharge). Research staff will perform phone visits using protocol in Appendix A8 at the approximate end of wks 1-6 to control for staff interaction and data collection. During wk 6, an exercise nurse intervener will make a phone visit to screen participant’s readiness to start intervention as described for IIG participants. Once participant is ready to start, nurse will arrange home visit within approximately 3 days. The exercise intervention and procedures will be identical to those received by the IIG group during wks 1-6. Staff contact WCG by phone (if too ill, data collection re-scheduled within approximately 3 days) to collect data at the end of approximately wks 7-12.

5C2b) ACG participants will have baseline data collected pre-surgery by a nurse recruiter and receive a pedometer and instructions for recording total steps/day in Daily Diary (Appendix A7). The ACG nurse intervener will visit in the hospital post-surgery to review study trajectory, make a phone visit within approximately 4 days of post-surgical discharge to initiate the ACG intervention (Appendix A3), and make phone visits at the start of approximately wks 2-6. During visits, the nurse will deliver the ACG intervention. Data collectors will contact ACG by phone within approximately 24 hrs of hospital discharge (if too ill, re-scheduled within approximately 3 days of discharge) and at the approximate end of each week for 6 wks to

obtain outcome measures.

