Perceived Self-Efficacy	CRF and Walking Self-management	PSE for Fatigue Self-Management (6 items), Walking Duration (12 items)	Pre & Post-Surgery Weeks 1-12	PSE for CRF self-management (.92) and PSE for walking duration (.95).
Perceived Self-Efficacy	Balance	Activities-specific Balance Confidence (16 items)	Pre & Post-Surgery Weeks 3, 6, 9, 12	PSE for balance for increasingly challenging activities (.82-.90).
CRF Self-Management Behaviors	Walking Exercise	Recorded in Daily Diary and electronically in the Wii Fit Plus	Weeks 1-12	Total number of minutes walked with the Wii per week.
CRF Self-Management Behaviors	Balance Exercise	Recorded in Daily Diary and electronically in the Wii Fit Plus	Weeks 1-12	Total number of balance exercises completed with the Wii per week.
Functional Status	Capacity	Fatigability; Six-minute Walk Test	Pre-Surgery, Prior to Chemo/Week 6, & 12	Degree of fatigue associated with walking during the six-minute walk test. Distance walked in six minutes.
Functional Status	Performance	SF-36 v2 – 8 subscales accounting for two components, physical and mental health (36 items)	Pre & Post-Surgery Weeks 3, 6, 9, 12	Performance of daily mental and physical activities that people do in the normal course of their lives (.78-.92)
Functional Status	Performance	Pedometer Daily Diary	Weeks 1-12	Performance in average number of steps taken per day per week
Quality of Life	Quality of Life	QOL Index: Overall QOL, Family, Health/Function, Socioeconomic, Psych/Spiritual (66 items)	Pre & Post Surgery Weeks 3, 6, 9, 12	Satisfaction with various aspects of life and the importance of each aspect of life to the person (.73-.99)

Legend: Surgery = Sx; CRF = Cancer-Related Fatigue. PSE = Perceived Self-Efficacy. Medical Outcomes Short Form-36 v2 = SF-36 v2. QOL = Quality of Life

Revision 5/19/2019. Updated Table with the following 3 measures added.

Table 3. Main Concepts, Variable, Measures, Collection Schedule, and Measurement Objective

Concept	Variable	Measure # Items	Schedule	Measurement Description (Cronbach's alpha)
Symptoms	Sleep Impairment	PROMIS v 1.0 Sleep-Related Impairment Short-Form 8a (8 Items)	Pre & Post-Surgery Weeks 3, 6, 9, 12	Degree of sleep-related impairment. (0.90)
Symptoms	Pain Source, Pain Treatment, Severity and Interference Information	The Brief Pain Inventory (4 Severity Items; 7 Interference items; 4 Source Items)	Pre & Post-Surgery Weeks 3, 6, 9, 12	Degree of pain severity and impact of pain on every day. living. (0.77 to 0.91)

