Perceived Self-Efficacy	Pain Self-Management	The Perceived Self-Efficacy for Pain Self-Management Inventory (6 Items)	Pre & Post-Surgery Weeks 3, 6, 9, 12	Degree of pain self-management. (0.90)

Aim 2 – Measures – WCG Delayed Intervention. At the start of wk 7, WCG will begin the intervention, concluding at wk 12. Aim 1 study variables and measures (Table 3) will be analyzed for Aim 2 for wks 7-12 to compare with the IIG wks 1-6 outcomes.

Aim 3 – Measures – IIG Intervention Sustainability. At the start of wk 7, IIG participants will be given the option to extend the intervention an additional 6 wks. We will measure the extension rate as % participants who elect to extend. Adherence to the intervention will be measured as % participating in the intervention who adhered to prescribed intervention. Weekly adherence will be calculated by taking number of times prescribed intervention was completed divided by total number of interventions prescribed for week. These data are recorded in the Daily Diary and will be confirmed by research staff reviewing recorded data in Wii Fit-Plus. Retention, measured as part of sustainment, will be calculated as % who elected to extend 6 wks who completed final data collection at wk 12. Based on our conceptual definition of sustainability, we will measure the extent to which components of the intervention were rated acceptable for continued use by participant. Acceptability will be measured at end of wk 6 and 12 using a 15-item Acceptability Questionnaire (Appendix B1) using a numeric scale (1 to 6: 6 = agrees strongly) with higher scores indicating greater acceptability of the exercise program. The Questionnaire has a Flesch-Kinkaid 6th grade reading level and was successfully used in our R21 RCT and allows participants to rate how well barriers and facilitators to exercise are addressed. Open-ended questions provide further input.^{23,24} Efficacy will be measured using the same study variables and measures analyzed in Aim 1 (Table 3) for wks 7-12.

Section 8.0 Drug Formulation and Procurement

Not applicable. This study is not a pharmaceutical trial.

Section 9.0 Toxicity and Adverse Event Reporting Guidelines

Study Monitoring

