AEs will be collected from the time the subject signs the consent form until 30 days after the final protocol specified intervention. All AEs will be followed until resolution or a cause is identified. AEs judged by the investigator as not related or probably not related to the treatment will NOT be followed beyond the end of the study.

Section 10.0 Statistical Considerations

Statistical Analysis. All tests of hypotheses will be two-tailed at $\alpha=0.05$. We compare groups at baseline using parametric and non-parametric tests to assess equivalence of confounding physiological and contextual patient characteristics, and pre-surgical outcome variables. If substantive differences exist, they will be controlled for in subsequent analyses by regression techniques, guided by the degree of dissimilarity rather than strict statistical significance.¹⁴⁴

Primary analysis (Aim 1) is the comparison among study groups of the primary outcome CRF severity and fatigability assessed at approximately 6 wks post-surgery. Analysis is based on a regression model for both CRF scores with the following variables in the regression equation: baseline CRF, study group, age, and (if appropriate) plausible interaction between these variables. We test association of study group with outcomes.

In Aim 2 our hypothesis comparing outcomes in IIG and WCG by age group will be addressed in the context of a longitudinal analysis. There are 6 time-ordered differences between IIG and WCG. We use generalized linear (mixed) models to allow flexible correlation structures in the repeated measures.^{145,146} Our regression equation has in addition to the aforementioned variables: time (week) of assessment, and critically, study group with time interactions. The model allows us to test if group effects are changing over time – referred to as a “parallel” profile analysis.¹⁴⁷ If the hypothesis is supported, we test whether that average profiles (over time) in

the two groups are the same. Aim 3 concerns three binary responses in the IIG group at 6 wks: extension, retention, and adherence. Logistic regression models will be used to assess the influence of explanatory variables on the likelihood of outcome.¹⁴⁷⁻¹⁴⁹

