Secondary Outcomes: An analogous strategy is applicable to continuous outcomes assessed at 12 wks. We will use linear models with the caveat that models are conditional on electing to extend participation. Statistical analysis will include intent-to-treat (ITT) analysis and per protocol analysis.^{150,151} ITT principle calls for making inference on the whole sample, with patients as randomized to their study group.¹⁵² To address missingness in our response data we will explore strategies for imputation.¹⁵³ The techniques described above allow missing at random (MAR). Inverse-probability weighting¹⁵⁴ will be investigated to accommodate missing data patterns that are not MAR. Assurance of analysis robustness and minimization of bias: We use a range of outcome measures based on the patient-centered principle to ensure the relevance of the study both biologically and practically. To enhance reproducibility, we will ensure protocol fidelity and follow our analytic plans, including addressing missing data in outcomes. To minimize analysis bias, we will adjust for factors such as potential between group unbalance and examine the robustness of our conclusions under deviations of model assumptions.

Note: Determination of Sample Size is discussed under the Research Design (Section 5, specifically, Section 5B)

TIMELINE. The research timeline is shown in Table 4.

POTENTIAL PROBLEMS AND ALTERNATIVE STRATEGIES. We acknowledge that NSCLC patients after surgery may be subject to complications requiring a break from the intervention. Should participants report unmanaged symptoms or clinical problems, they will be referred to their health care provider per protocol. Should the participant become ill, causing them to miss three consecutive exercise interventions, the participant will be instructed to call their nurse, who will reevaluate and adjust the exercise prescription per protocol. Should the primary nurse intervener become ill or unable to meet with participant, a pre-assigned secondary nurse intervener will step in. There could be diffusion of treatment effects between IIG, WCG, and ACG as well as confounding effects if a disproportionate number of physically active participants are assigned to the IIG, WCG, or ACG. We will assess functional capacity levels and use block randomization to minimize these effects.

Table 4. Research Timeline	Year 1				Year 2				Year 3				Year 4				Year 5			
Activities	Q1	Q2	Q3	Q4																

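### Aim 2's two windows share no week since discharge, so the comparison does not account for time since surgery and cannot separate start time from recovery

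*Combined protocol and SAP*

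**What the plan says.** Section 5A evaluates timing by comparing IIG outcomes in weeks 1-6 with those of WCG in "wks 7-12 by age to account for time since surgery". Section 7.0 (Aim 2 - Measures) repeats the windows: the Aim 1 variables "will be analyzed for Aim 2 for wks 7-12 to compare with the IIG wks 1-6 outcomes". Hypothesis 2 (Section 1.0) predicts that IIG improves both faster and by more, on every outcome.

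Section 10.0 fits a longitudinal model with baseline CRF, group, age, week of assessment and group-by-week terms, and states "There are 6 time-ordered differences between IIG and WCG". Parallelism is tested first; then "If the hypothesis is supported, we test whether that average profiles (over time) in" the two groups agree. Whether week counts from discharge or from the start of exercise is not stated.

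Four other provisions bear on this:
- Section 5C2b: ACG outcomes are collected by phone "at the approximate end of each week for 6 wks to" obtain the measures. No later ACG collection is planned.
- Table 3: the six-minute walk test (6MWT) is scheduled "Pre-Surgery, Prior to Chemo/Week 6, & 12"; SF-36 and balance are scheduled "Pre & Post-Surgery Weeks 3, 6, 9, 12".
- Section 10.0: the 12-week "models are conditional on electing to extend participation".
- Section 5C1a has IIG exercising in weeks 1-12, whereas Section 5C2 makes the second six weeks optional.

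**The concern.** Optimal timing is one of the trial's three aims. Patients recovering from lung surgery change over twelve weeks whether or not they exercise. Section 5A also says that adjuvant treatment commonly begins 4-10 weeks after surgery, in nearly 30% of patients, so it can fall differently in the two windows. Section 10.0 names no term for it. If IIG is always observed early and WCG always late, either influence can appear as a group difference and be reported as an effect of start time. The text tells the reader that this has been dealt with.

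**Working it through.** **1. Overlap.** The week sets {1,...,6} and {7,...,12} have no member in common. Six paired differences imply exercise week as the clock. Then

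week since discharge = exercise week + 6 x (1 if WCG, 0 if IIG).

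- Intercept, arm, exercise week and week since discharge: rank 3 of 4.
- Arm plus 12 week-since-discharge indicators, planned data: rank 12 of 13.
- The same columns using weeks 1-12 of both arms: rank 13 of 13.

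The rank result restates the lack of overlap. It also shows that the missing information lies in the weeks that Aim 2 leaves out. Splitting by age gives two strata with the same gap. Pre-surgery baseline has the same expected value in both randomised arms, so adjusting for it cannot remove the offset.

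**2. Does anything change without exercise?** Pilot usual care, post-surgery to week 6 (Section 2N, Functional Performance paragraph included):
- symptom severity 4.9 (SD 1.6) to 3.8 (SD 1.5): 1.1 points better;
- symptom interference 4.5 (SD 2.8) to 2.9 (SD 2.3): 1.6 points better;
- SF-36 physical 32.7 to 38.8: 6.1 points better.

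**3. Expected differences when start time has no effect.** The plan gives no Aim 2 power or effect size to reproduce. Let R be the six-week recovery and f the share of R repeated in weeks 7-12. The documents do not give f, so a range is used. With linear recovery, the mean gain over weeks 1-6 is R x 3.5/6, and over weeks 7-12 it is R + fR x 3.5/6.
- Average severity, IIG minus WCG = 1.1 x (1 - 3.5/6) + f x 1.1 x 3.5/6 = 0.46 + 0.64f. This gives +0.46, +0.78 and +1.10 for f = 0, 0.5 and 1 (IIG worse).
- Extra six-week SF-36 physical gain in IIG = 6.1 x (1 - f) = 6.1, 3.05 and 0 (IIG better).

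**4. The Section 10.0 test sequence, simulated.** Assumptions: 60 per arm, the same linear exercise effect in both arms, constant SD (1.6 severity, 2.8 interference), no baseline covariate and 6,000 trials per cell. Parallelism is a Hotelling T-squared test on five successive differences. The average-profile test counts only when parallelism is not rejected. The three figures per cell are for within-person correlation exchangeable 0.5, exchangeable 0.7 and AR(1) 0.8.

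| f | Outcome | Parallelism rejected, % | Average test favours WCG, % |
|---|---|---|---|
| 0 | severity | 81 / 97 / 51 | 10 / 2 / 23 |
| 0 | interference | 63 / 87 / 35 | 15 / 4 / 23 |
| 0.5 | severity | 23 / 40 / 14 | 72 / 52 / 77 |
| 0.5 | interference | 18 / 28 / 11 | 68 / 52 / 68 |
| 1 | severity | 5 / 5 / 5 | 95 / 95 / 94 |
| 1 | interference | 5 / 5 / 5 | 94 / 90 / 92 |

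At f = 0 the departure from parallelism is IIG appearing to improve faster. The average test favoured IIG in 0.0% of trials in every cell.

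**5. A hand check on the end-of-exercise level.** For severity at f = 0.5 the expected difference is 0.55. With the week-6 SD of 1.5, 0.55 / (1.5 x sqrt(2/60)) = 2.01, and Phi(2.01 - 1.96) is about 0.52. At f = 1 the rejection rate is 98%.

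**6. CRF severity.** The usual-care post-surgery mean is not in the text. Joining the exercise arm's post-surgery 4.1 to usual care's week-6 4.0 gives R = 0.1. With SD 2.0, parallelism then rejects in 4.6-5.4%, and the average test favours WCG in 2.9-5.5% (nominal 2.5%) and IIG in 0.9-1.8%. If CRF instead fell by an assumed 0.25, 0.5 or 1.0 points between weeks 6 and 12, a simple end-of-exercise test would reject in 10.5%, 28% or 78%.

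**7. Number of time points.** Six differences exist only for weekly measures. SF-36 and balance give three points per exercise period if the start value is counted. For fatigability, WCG has a 6MWT at week 6, just before it starts exercising. IIG has none between surgery and week 6, so a rate of improvement over the exercise period cannot be compared.

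**The case against.** The arms are randomised and each is observed over an equal planned six weeks of exercise. A later position in recovery is part of what a late start means. This stands: the contrast is a valid description of outcomes during exercise under two start times. A reader might infer that it can say nothing about timing, which goes too far. What it cannot do is isolate start time from recovery or adjuvant treatment.

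The clock is inferred, because Section 10.0 does not state it. That is true, but Sections 5A and 7.0 fix the windows, and no choice of clock makes them overlap.

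A reader might add the two rejection rates into one false-positive rate. They point in opposite directions, so the sum is not the error rate of any claim in Hypothesis 2. A reader might also infer that usual care worsened on some measures, since symptom count rose from 6.6 to 7.4 (SD 3.3, n = 35). With an assumed within-person correlation of 0.3-0.7, t = 0.8 / (3.3 x sqrt(2(1 - r)/35)) is only about 1.2-1.9.

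The strongest objection is to the week-12 alternative: it exchanges recovery confounding for unequal exercise. Suppose there is no timing effect, the exercise effect is 2.0 points, and half of IIG extend and gain a further 25%, 50% or 100% of it (assumed). The mean shift is 0.25, 0.5 or 1.0 points, and the week-12 test rejects in about 10%, 28% or 78%. This also stands. The week-12 comparison should therefore be added as a comparison of start policies and not presented as a clean timing test.

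**Conclusion.** The statement that the comparison accounts for time since surgery is wrong as written. Arm and time since discharge are fully aliased at each exercise week, and nothing in the planned Aim 2 data separates them. For symptom severity and interference, recovery alone can make IIG appear to improve faster (35-97% if it stops at week 6) or make WCG appear better on average (90-95% if it continues fully). These figures assume linear recovery, constant SD, the stated correlations and an equal exercise effect.

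A reader might infer that Aim 2 would falsely confirm Hypothesis 2 on all outcomes, or that CRF severity is badly affected. The documents support neither. The direction depends on the measure and on f, and no material inflation is shown for CRF severity, although that rests on a proxy that crosses arms. Aim 1 compares the arms at the same week and is unaffected. This should be fixed, but it does not undermine the trial's primary comparison.

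**What to change.** 1. Delete the phrase about time since surgery in Section 5A, and state in Section 10.0 that the Aim 2 clock is exercise week.
2. Report IIG weeks 1-6 against WCG weeks 7-12 as a description of outcomes during each exercise period, and do not attribute a difference to start time alone.
3. Add the randomised same-week comparison, IIG against WCG at week 12, from a mixed model on weeks since discharge. For fatigability use week 12 adjusted for pre-surgery. Include all randomised IIG participants whose data are collected, without Section 10.0's condition on extending. Report how many non-extenders have week-12 data, and treat the rest as missing with a sensitivity analysis. Word the result as a comparison of start policies with unequal total exercise (up to 12 against 6 weeks).
4. Reconcile Section 5C1a with Section 5C2 on IIG weeks 7-12, so that the IIG policy is defined.

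**Cost.** Mostly wording. Figure 8 schedules weeks 7-12 data and a week-12 6MWT in both arms. However, Section 5C2 places the IIG collection directly after the extension option, and Section 7.0 defines week-12 retention among extenders only, so non-extenders may need added calls and a 6MWT. Visits already missed cannot be recovered.

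A week-12 level tests magnitude and not rate, and exercise dose differs between arms. With SD 2.0, the difference detectable with 80% power is 2.80 x 2.0 x sqrt(1/60 + 1/60) = 1.02 CRF points. If only half of IIG is assessed, it is 2.80 x 2.0 x sqrt(1/30 + 1/60) = 1.25, and the comparison is then no longer as randomised. Hypothesis 3 expects only that more than 50% will extend, so that case is not remote.

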5B) Setting & Sample. The target sample will be recruited in **5 sites**. We will continue the working relationships we built while conducting our R21 RCT with Spectrum Health, McLaren, and Sparrow Health. We will add Munson Healthcare and Nebraska Medicine Campus. Results from our R21 RCT show very large effect sizes between the exercise and usual care groups that are not expected to hold in this proposed study as we have additional sites with more diverse populations and two new study arms (ACG and WCG). Our sample size assessment for primary Aim 1 uses the expected CRF severity scores by age group shown in **Table 1 (below)** with CRF estimates from our R21 RCT for comparison. An exemplar multiple regression model was run with age distribution approximating the NSCLC population with 33% < 65 yrs and 67% ≥ 65 yrs, model error standard deviation (SD) = 2.0. Comparable R21 results suggest a SD between 0.7 and 2.6 in these two age groups. With overall significance level at 5%, we computed the total sample size N to ensure at least 80% power in 4 pre-specified comparisons between IIG and ACG for ages <65 and ≥ 65. With N = 180 (60/group, 20 <65 yrs and 40 ≥ 65 yrs) power to detect the expected CRF is shown in **Table 2 (below)** with the minimum sample size for each comparison. Based on our R21 RCT and previous cancer work,¹¹⁵ we will over-recruit to account for a conservative attrition rate of 20% (N = 225 = 180/0.8), and under plausible assumptions,^{116,117} conservatively provide for 90% compliance increasing for a total of N = 279 ≈ 225/(0.9)(0.9)¹¹⁷ patients.

Table 1: Expected mean CRF Severity scores at 6 weeks post-surgery by age

Group	Age	CRF-Expected	CRF-from R21
IIG	<65	2.5	0.81
IIG	65+	2.0	0.68
WCG	<65	4.5	4.12
WCG	65+	4.2	3.99
ACG	<65	4.3	4.12
ACG	65+	4.0	3.99

Table 2: Power to detect expected differences in mean CRF Severity scores between groups by age

Comparison	Age	Power (N=180)	N for 80% power
IIG vs ACG	<65	0.81	180
IIG vs WCG	<65	0.88	144
IIG vs ACG	65+	0.94	81
IIG vs WCG	65+	>0.99	63

5C) Study Protocol

The following protocol was used successfully in our R21 RCT with the addition of the WCG and ACG in the proposed study. Participants scheduled for NSCLC surgery will be identified by the surgeon's office prior to surgery, recruited, and enrolled by the nurse recruiter.

5C1) Study Interventions.

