
Section 6.0 Measurement of Effect

As earlier stated following our Specific Aims and Hypothesis, based on existing evidence,⁷²⁻⁷⁵ results of our single-arm pilot (no control group)^{76,77} and two-arm R21 RCT,²³ we expect the benefits of this study to confirm that post-surgical NSCLC patients will find the exercise intervention effective in reducing CRF severity and fatigability (functional capacity). Further, we expect the exercise intervention group will outperform the attention control and wait-list control groups by age for other symptoms' severity; PSE for CRF self-management; PSE for walking; PSE for balance; functional performance; and QOL. We expect the wait-list exercise intervention group's CRF severity and fatigability to improve, but not as significantly as the immediate exercise intervention group. We also expect >50% of the immediate exercise intervention group to extend 6 more wks, with adherence and retention rates of >70% at wk 12, with improved primary and secondary outcomes at wk 12.

Section 7.0 Study Parameters

Measures for Aims 1-3. Aim 1 - Measurement IIG v. ACG and IIG v. WCG Comparisons. Table 3 depicts main study variables and corresponding measures embedded in the concepts of the theoretical framework in Fig 1 (see measures Appendix B1-B9). All measures are administered to all participants using the schedule in Table 3. Participant characteristics as depicted in Table 3 describe the sample. Age is a key biological variable. Given that lung cancer and CRF are significant problems for persons of all ages, and an exercise intervention must be applicable to patients of all ages, study variables will be analyzed for participants by age (< 65 and \geq 65). Also, this study includes men and women as lung cancer is the second most common diagnosed solid tumor with CRF a common symptom for both.¹²⁸ All primary and secondary outcome measures have well established psychometrics, both validity and reliability, with internal consistency scores reported in Table 3 for the cancer

population including use in post-surgical NSCLC.²³⁻²⁴ All measures were used successfully in the R21 RCT without participant complaint about burden. The Karnofsky Performance Scale provides functional impairment classification, universally used in oncology, and is scored from 0% (dead) to 100% (no complaints).¹²⁹

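### Section 5B claims an overall 5% level across four comparisons, but Table 2 spends 5% on each with no rule to hold the overall level; separately, its printed power of 0.94 should be 0.99

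*Combined protocol and SAP*

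**What the plan says.** Section 5B bases the sample size on this sentence: "With overall significance level at 5%, we computed the total sample size N to ensure at least 80% power in 4 pre-specified comparisons". The sentence goes on to describe them as "pre-specified comparisons between IIG and ACG for ages <65" and for 65 and over. Table 2, however, lists IIG vs ACG and IIG vs WCG in each age group, and gives power at N = 180 "with the minimum sample size for each comparison". Section 7.0 agrees with Table 2: its Aim 1 heading is "Measurement IIG v. ACG and IIG v. WCG Comparisons", and it says that "study variables will be analyzed for participants by age".

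Section 10.0 says "All tests of hypotheses will be two-tailed at" 0.05. Its primary analysis is a regression of the week-6 score on baseline, study group and age, with interactions only where appropriate, followed by a test of the study-group association. CRF severity and fatigability are both named as primary. Neither section gives an adjustment, a testing order or a success criterion for the four comparisons.

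**The concern.** An overall 5% level over four comparisons and an unadjusted 5% level for each one are different promises. They agree only if the trial claims success solely when all four comparisons succeed, and neither 5B nor Section 10.0 says so. Without a stated rule, neither the error rate behind a claim for one age group against one control nor the power to make that claim is defined. It would have to be settled after the data are in, when the choice could decide which by-age claims are made.

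Two smaller faults sit in the same place. One printed power does not follow from the plan's own inputs, and the text misdescribes two of the four comparisons.

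**Working it through.** **Inputs (Section 5B, Table 1).** Error SD 2.0. N = 180 in three equal arms, with 20 per arm under 65 and 40 per arm at 65+. Six cells, so error df = 180 − 6 = 174. Expected differences (control minus IIG): ACG under 65, 4.3 − 2.5 = 1.8; WCG under 65, 4.5 − 2.5 = 2.0; ACG 65+, 4.0 − 2.0 = 2.0; WCG 65+, 4.2 − 2.0 = 2.2.

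**Step 1: reproduce Table 2.** The noncentrality is λ = Δ / (2.0 × √(2/n)). Power is the probability that a noncentral t with 174 df exceeds the two-sided critical value in absolute size. The minimum N moves in steps of 9, which keeps 1:1:1 allocation and the 1:2 age split; df = N − 6.

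| Comparison | Δ | n/arm | λ | Power at 0.05 | Table 2 power | Min N at 0.05 | Table 2 N | Power at 0.0125 | Min N at 0.0125 |
|---|---|---|---|---|---|---|---|---|---|
| IIG vs ACG, <65 | 1.8 | 20 | 2.85 | 0.808 | 0.81 | 180 | 180 | 0.627 | 252 |
| IIG vs WCG, <65 | 2.0 | 20 | 3.16 | 0.882 | 0.88 | 144 | 144 | 0.738 | 207 |
| IIG vs ACG, 65+ | 2.0 | 40 | 4.47 | 0.994 | 0.94 | 81 | 81 | 0.973 | 108 |
| IIG vs WCG, 65+ | 2.2 | 40 | 4.92 | 0.998 | >0.99 | 63 | 63 | 0.991 | 90 |

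The N column matches exactly at 5% per comparison and not at 5%/4. Table 2 therefore spends 5% four times.

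**Step 2: the 0.94.** No variant tried gives 0.94 with 40 per arm and SD 2.0: pooled t 0.994, separate two-sample t 0.993, one-sided 0.998, Bonferroni 0.973. A power of 0.94 at this difference corresponds to about 25 per arm. The same row's N of 81 fits the stated inputs, so only the power entry is wrong.

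**Step 3: what four unadjusted tests deliver.** Simulation at N = 180 (400,000 trials, shared IIG arm, pooled variance):
- Any single win may be claimed: at least one false positive under the global null in 17.2% of trials, or 8.8% counting only false wins for exercise.
- All four must succeed: a false claim for exercise occurs at most 2.5% of the time. Joint power for CRF severity is 0.74.

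**Step 4: Holm at an overall 5%.** The ordered p-values are compared with 0.05/4, 0.05/3, 0.05/2 and 0.05. Powers in Table 2 order are 0.78, 0.85, 0.99 and >0.99, with family-wise error 4.7%. For the comparison that sets N, Hochberg gives 0.79 and plain Bonferroni 0.63. Under Holm, N = 189 would bring it to 0.80.

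**Step 5: could the group test protect the comparisons?** Suppose the group test must be significant first, followed by unadjusted tests.
- Age-pooled comparisons, 2-df group test: error is 4.2% under the null and 5.0% if only WCG differs, so 5% is held. The pooled differences are (1.8 + 2 × 2.0)/3 = 1.93 and (2.0 + 2 × 2.2)/3 = 2.13, with power above 0.99 even at 0.0125.
- By-age comparisons with an effect only at 65+: false wins under 65 are 8.6% after a 2-df test and 9.1% after a 4-df test, against 4.6% with Holm.

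Only the by-age claims are therefore exposed, but these are the claims that set N.

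**Step 6: sensitivity (Holm power for the weakest comparison / joint power of unadjusted tests).** At N = 180: 0.96/0.96 at SD 1.5, 0.78/0.74 at SD 2.0, 0.52/0.43 at SD 2.6. Section 5B gives the range itself: "Comparable R21 results suggest a SD between 0.7 and 2.6 in these two age groups". With 279 enrolled, and assuming that non-adherence shrinks the effect in proportion, the plan's 20% attrition and 90% compliance give 0.79 and 0.74 to 0.75. Retention of about 83% at 90% compliance brings Holm to 0.80. The R21 rates (97% retention, 93% adherence) give 0.89 and 0.87.

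**The case against.** The strongest reply is that the shortfall depends on Holm, which the plan does not mention. That is right. A closed test that uses the summed contrast for each intersection holds the overall level by construction. In simulation at N = 180 it gives 0.802, 0.868, 0.993 and 0.998, so the 5B sentence can be met under Table 1, at the price of less power if effects are uneven across ages or controls. The documents thus do not show that 80% is unattainable. They show that no method is named and that the printed table is unadjusted.

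A second reply is that Hypothesis 1 in Section 1.0 expects exercise to beat both controls at all ages, which reads as an all-four requirement. On that reading, unadjusted tests do hold the level and the joint power of 0.74 contradicts nothing printed. But the hypothesis is a prediction, not a decision rule, and it also spans fatigability and every secondary outcome, so 0.74 is not its power.

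Third, the confirmatory test may be the age-pooled group effect, where error and power are both sound. That leaves the four comparisons on which N was built without a stated role.

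Finally, SD 2.0 may be cautious: the R21 week-6 SDs of 0.7 (n = 37) and 2.0 (n = 35) in Section 2N pool to √((36 × 0.49 + 34 × 4.0)/70) = 1.48. That eases the concern about power but not the one about error rate, and 5B's own range runs up to 2.6.

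**Conclusion.** The concern holds. Table 2 rests on 5% per comparison, while the text claims 5% overall. Separate tests at 0.05 deliver the overall level only if all four must succeed, and no such rule is stated.

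The consequence depends on the rule: about 17% family-wise error if any win counts; a shortfall of about 2 points (0.78 against 0.80) for one comparison under Holm; or an unreported joint power of 0.74 under an all-four rule. These figures assume Table 1's means, SD 2.0 and 180 evaluable participants, and they concern CRF severity only.

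The 0.94 is wrong under every rule, but it errs on the safe side and does not affect N. This should be fixed before analysis; it does not call the size of the trial into question.

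**What to change.** Keep N = 180 evaluable.

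1. In 5B and Section 10.0, name the four CRF-severity comparisons (IIG vs ACG and IIG vs WCG, each under 65 and at 65+), replacing the description that mentions ACG only. State one rule in both places: either Holm at an overall two-sided 5%, if separate claims by age and control are wanted, or an explicit requirement that all four succeed. Another pre-specified procedure that holds the level would also serve, with power quoted under it.
2. Restate Table 2 and the 80% sentence under the chosen rule: 0.78/0.85/0.99/>0.99 for Holm, or 0.81/0.88/0.99/>0.99 with joint power 0.74 for the all-four rule.
3. Correct 0.94 to 0.99 for IIG vs ACG at 65+.
4. Say whether fatigability falls inside or outside the overall 5%. The method is the sponsor's choice.

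The cost is wording, with no extra patients. The price is a slightly less favourable stated power: 0.78 rather than 0.81 for the comparison that sets N under Holm, or a reported joint power of 0.74 under the all-four rule.
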